Part B will be undertaken using the modified toxicity probability interval (mTPI) method. The mTPI design uses a Bayesian decision framework to inform dose-escalation and dose de-escalation decisions. A target DLT rate of 25% with an equivalence interval (20% to 30%) will be used to estimate the maximum tolerated dose (MTD) of the combination regimen during dose escalation. For all UCB6114 dose levels, enrolled participants will be treated in cohorts of 2 to 4 participants (target of 3), who can be treated in parallel. Each UCB6114 dose level may have more than one cohort and will have a minimum of 3 and a maximum of 9 evaluable participants. For further detail on the mTPI method, the calculated model-based dose-escalation/dose de-escalation decisions to help inform the Safety Monitoring Committee (SMC)'s decision, and the determination of the MTD, please refer to Section 4.1.3.2.2 of the protocol. Detail on the operating characteristics for the mTPI design is included in [Section 2.4](#) below.

[figure not shown]
The planned duration of study treatment during Part B is 2 cycles. Participants may remain on study for additional cycles if they are receiving therapeutic benefit or until they fulfill one of the criteria for study discontinuation. Participants will continue treatment until disease progression, unmanageable toxicity, or withdrawal of consent. Upon discontinuation of treatment, participants will be referred to appropriate follow-up care per the investigator's judgment.

From Part B, a recommended Phase 2 dose for UCB6114 in combination with TFD/TPI (RP2D-T) will be determined based upon the totality of information, including the safety profile, PK data, PD biomarker data, and available antitumor activity.

Part B of the study is planned to be conducted at study sites in the United Kingdom (UK) and United States (US).

A schematic diagram of Part B of the study is provided in [Figure 2-1](#).

Figure 2-1: Study Schematic for Part B

bid=twice daily; D=Day; DLT=dose-limiting toxicity; iv=intravenous; mTPI= modified toxicity probability interval; po=oral; TFD/TPI=trifluridine/tipiracil

*Dose must not exceed 80mg/dose

Notes: A dose may be given in more than 1 cohort

Escalation to the next dose level or de-escalation to the previous dose level will be guided by the mTPI algorithm.

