8.2 Adverse events

The primary safety endpoints for Part B of this study are the incidence and severity of TEAEs (including SAEs) from the first dose of UCB6114 treatment on Day 1 of Cycle 1 until the end of the SFU Period (up to 30 days following the last dose of UCB6114 treatment), and the incidence of DLTs from the first dose of UCB6114 on Day 1 of Cycle 1 until the end of the 28-day DLT Observation Period (Day 28 of Cycle 1).

All AEs in Part B of the study will be coded using MedDRA® and classified as pre-treatment and treatment-emergent relative to the first dose of UCB6114 treatment. Adverse events with a start date prior to the first infusion of UCB6114 will be defined as pre-treatment AEs. A TEAE is defined as any AE with a start date on or after the first dose of UCB6114 up until the last dose of UCB6114 + 30 days. A pre-treatment AE which increases in severity on or after the first dose of UCB6114 will also be counted as a TEAE. Note that in this case, the pre-existing AE will have a stop date and an outcome of ‘worsened’ and a new AE (with the same verbatim) will be entered with the same start date and the increased severity recorded on the eCRF. Any AE (including SAEs) with an onset date later than the last dose of UCB6114 + 30 days will not be considered as treatment-emergent and therefore will not be included in the tabulations of TEAEs. These AEs will be considered as post-study AEs and will be listed only. Where onset dates are missing or partially missing, AEs will be assumed to be treatment-emergent, unless there is clear evidence to suggest that the AE started prior to the first dose of UCB6114 and it has not increased in severity. Missing or partially missing dates for AEs will be handled as described in [Section 4.2.3](#) All AEs for a participant will be recorded in the eCRF from the time of informed consent until completion or early discontinuation of Part B of this study. Serious adverse events are to be reported up to 30 days after the Final Visit (i.e. up to 150 days after the last dose of study treatment).

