Overall survival (OS) will be calculated as the time in days from the date of first dose of UCB6114 to the date of death from any cause. Participants will be followed up to ascertain their survival status at the SFU visit (within 30 days after their last dose of UCB6114) and at the Final Visit (3 months after their last dose of UCB6114); they will not be followed up beyond this timepoint.

The following calculation will be performed:

$$OS = (Date of Death - Date of First Dose of UCB6114) + 1$$

OS will be censored on the date of their last contact for participants who discontinue early from Part B of the study or who discontinue study treatment due to disease progression but continue in the study, and are not known to have died.

Further details on the rules to apply in the derivation of OS are included in the Derivation of Efficacy Endpoints document which has been developed to support this SAP.

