Duration of confirmed response, DOR (confirmed or unconfirmed) and PFS will be listed and summarized descriptively using Kaplan-Meier estimation. These summaries will be repeated for the sensitivity analyses of these endpoints (defined in [Section 10.1.1](#) above) and will include the number and percentage of participants with the event, the number and percentage of participants censored, minimum and maximum values and Kaplan-Meier estimates of the 25th percentile, median, 75th percentile and corresponding 95% CIs calculated using Greenwood's formula. In addition, DOR and PFS rates at 3 months, 6 months and 9 months will be derived from the Kaplan-Meier estimation and presented together with associated 95% CIs.

Kaplan-Meier curves will be presented for duration of confirmed response and DOR (confirmed or unconfirmed) and PFS. Treatment groups will be overlaid on each plot.

Survival status collected on the eCRF at the SFU visit and at the Final Visit will be listed for each participant by treatment group. This listing will include the participant's survival status, date and cause of death, whether an autopsy was performed and date of autopsy, whether the participant had received any further antitumor treatment after the last dose of study treatment and the type of treatment, and whether the participant's disease had been assessed since the end of study treatment including method of assessment and the overall response.

Overall survival times will be listed and summarized descriptively using Kaplan-Meier estimation. Note that since participants are only followed up for survival until the Final Visit in Part B of the study, a summary of OS may not be meaningful (i.e. if no participants die then OS cannot be assessed).

Exploratory analyses of selected antitumor activity endpoints may be performed based on subgroups of participants in the SS. Data permitting, the subgroups will be defined based on participant, disease, and treatment history information (e.g. extent of prior anti-cancer therapy).

Additionally, the relationship of the antitumor activity variables with key PK parameters may be explored but this will be reported separately.

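### In Parts B and C, OS censoring is tied to progression, so a Kaplan-Meier OS estimate beyond 3 months from first dose is informatively censored

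*SAP*

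**What the plan says.** Section 2.3 of the Part B SAP ties the end of treatment mainly to the disease: "Participants will continue treatment until disease progression, unmanageable toxicity, or withdrawal of consent". Section 10.1.1 then fixes survival ascertainment at the Safety Follow-up visit and at the Final Visit, 3 months after the last UCB6114 dose, and adds of participants that "they will not be followed up beyond this timepoint". Its censoring rule reads "OS will be censored on the date of their last contact for participants who discontinue early from Part B of the study", and extends to those "who discontinue study treatment due to disease progression but continue in the study, and are not known to have died".

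Section 10.1.2 plans the analysis: "Overall survival times will be listed and summarized descriptively using Kaplan-Meier estimation". No time limit is set. The caveat that follows points to survival follow-up stopping at the Final Visit and concludes that "a summary of OS may not be meaningful (i.e. if no participants die then OS cannot be assessed").

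Section 8.2 sets a different horizon for serious adverse events, 30 days beyond the Final Visit, "i.e. up to 150 days after the last dose of study treatment".

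The Part C SAP has the same follow-up rule, Kaplan-Meier sentence and caveat in its Sections 10.1.1 and 10.1.2.

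**The concern.** Kaplan-Meier needs the participants censored at a given time to have the same future risk of death as those who stay under observation. Here the design itself decides who is censored. Progression ends treatment, the last dose starts a 3-month clock, and a living participant leaves the risk set when it runs out. From then on the curve describes people still on treatment or recently off it, and participants who progressed earlier are no longer represented.

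OS is a listed antitumor activity endpoint in both modules, and available antitumor activity is one input to the recommended Phase 2 dose. A median or late OS rate from so few participants is easily set beside outside figures, and nothing in the SAP would warn the reader that its later part is not a valid estimate of survival.

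**Working it through.** The SAP gives no OS rate, median, hazard or event count, so there is no figure to reproduce. The check has a part that follows from the documents and a part that rests on assumed hazards.

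**1. Censoring time (from the SAP).** Let P be the time from first dose to progression. Assume the last dose falls about a week (0.25 month) before progression is documented. A survivor is then censored at about P − 0.25 + 3 = P + 2.75 months. The last dose cannot precede the first, so nobody who stays in the study is censored before 3 months. Up to that point there is no bias.

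**2. Who is left at 9 months (assumed hazards).** Take median time to progression 3 months, to death without progression 24, and to death after progression 6. Monthly hazards are a = ln2/3 = 0.2310, d = ln2/24 = 0.0289 and b = ln2/6 = 0.1155.

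- Alive, not progressed: exp(−(a+d)t) = 0.0964
- Alive, progressed: a/(a+d−b) × [exp(−bt) − exp(−(a+d)t)] = 1.60 × (0.3536 − 0.0964) = 0.4115
- True OS: 0.0964 + 0.4115 = 0.508
- Progressed and still observed (within the last 2.75 months): 1.60 × [exp(0.1444 × 2.75) − 1] × 0.0964 = 0.780 × 0.0964 = 0.0752
- Share of the living still observed: (0.0964 + 0.0752)/0.508 = 34%

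**3. Effect on the estimate.** The death hazard among all living at 9 months is (0.0289 × 0.0964 + 0.1155 × 0.4115)/0.508 = 0.099 per month. Among those observed it is (0.0289 + 0.1155 × 0.780)/1.780 = 0.0669, constant after 3 months. So:

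- 6 months: Kaplan-Meier 0.856 × exp(−0.0669 × 3) = 0.70; true 0.674
- 9 months: Kaplan-Meier 0.856 × exp(−0.0669 × 6) = 0.573; true 0.508

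A simulation of 400,000 participants agrees: 85.7% for both at 3 months, 70.1% against 67.4% at 6, 57.5% against 50.8% at 9, and 47.1% against 37.4% at 12. The median is 11.1 against 9.2 months, with 65% censored.

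**4. Range and direction.**

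- Eight exponential scenarios (median to progression 2 to 6 months, after progression 4 to 9, death without progression 24): about +2 to +4 points at 6 months and +4 to +8 at 9; median +0.8 to +3.0 months.
- Six others (median on treatment 2 or 3.5 months, after progression 3, 5 or 8, on-treatment death 1% per month, last dose at progression): about +2 to +4 points at 6 months and +6 to +9 at 9.
- Equal hazards before and after progression (d = b): no bias, because the observed hazard in step 3 equals b whatever the mix.
- Death more likely before progression than after (medians 3/4/6): 26.2% against 28.8% at 9 months, so downward.
- Post-progression deaths front-loaded (Weibull shape 0.7): 52.1% against 50.9% at 9 months. With shape 0.5: 48.6% against 50.8%, again downward.

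**5. The 150-day SAE horizon.** Suppose deaths up to 150 days (about 5 months) after the last dose count as events while survivors are censored at 3 months. The six scenarios above then give Kaplan-Meier below true OS, by about 2 to 6 points at 6 months and 1 to 11 at 9. If deaths and survivors are both followed to 5 months, the step 2 case gives 52.9% against 50.8% at 9 months and a median of 9.7 against 9.2: smaller, but not gone. Section 8.2 also implies a Final Visit at 150 − 30 = 120 days, whereas Section 10.1.1 says 3 months.

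**6. Numbers at risk.** In the step 2 case, 27 participants leave about 10 at risk at 6 months and 27 × (0.0964 + 0.0752) = 4.6 at 9. A dose level of 9 leaves about 3.4 and 1.5.

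**The case against.** The strongest reply is that little rides on this. OS is exploratory and descriptive, with 3 to 9 evaluable participants per dose level. At n = 9 and 67.4% survival, even without censoring, the 95% half-width is about 1.96 × √(0.674 × 0.326/9) = 31 points, against 2 to 4 points of bias at 6 months. Escalation is driven by DLTs, and no OS threshold enters the dose recommendation. All of this stands and limits the weight. It does not make the later estimates valid, since more participants would shrink the noise and leave the dependence on progression.

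Three stronger readings are tempting, and the documents do not support them:

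- A reader might infer that an OS median, OS rates at later months and an OS curve are promised. Section 10.1.2 specifies percentiles, the 3-, 6- and 9-month rates and curves for DOR and PFS. For OS it has one general sentence, qualified by whether the data allow it. What stands is that nothing excludes those outputs, and an unlimited Kaplan-Meier summary would normally include a median.
- A reader might infer that the SAP overlooks the short follow-up. Its caveat names it. But the only instance given is that nobody dies, whereas a distorted estimate appears when some do.
- A reader might infer that OS will be overstated. That needs a higher death hazard after progression, and beyond the window, than among those still observed. The documents give no hazards, and steps 4 and 5 show the bias disappearing or reversing.

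Further OS derivation rules sit in a supporting document that is not available here. It may settle how deaths after the Final Visit are treated.

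**Conclusion.** The point holds as a matter of design. In both parts OS censoring follows progression by about 3 months, so Kaplan-Meier OS beyond 3 months from first dose is informatively censored, and the existing caveat does not recognise this. Up to 3 months the estimate is sound, except for participants withdrawn or lost.

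The size is illustrative: about 2 to 4 points upward at 6 months and 4 to 9 at 9 months, if hazards are exponential and higher after progression than before. The sign is not established by the documents. It also depends on whether deaths known only through SAE reporting count.

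A reader might further infer that dose levels whose progressors live past 3 months are flattered most. This is not shown. In the scenarios with 2 months' median on treatment, lengthening median post-progression survival from 3 to 5 to 8 months lowers the 6-month bias from 3.7 to 3.1 to 2.2 points; only the shift in the median grows.

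Severity is low to moderate, because OS is exploratory and descriptive and dose levels are small.

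**What to change.** In Section 10.1.2 of both SAPs:

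- Limit the OS summary to the number of deaths and the Kaplan-Meier OS rate at 3 months from first dose.
- Report no OS median, other percentile or later rate, and truncate any OS curve at 3 months.
- Keep the OS listing.
- Extend the caveat to say that follow-up ends 3 months after the last dose, so later observation is censored in relation to progression, whether or not deaths occur.

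In Section 10.1.1 of both, state one ascertainment cut-off that applies equally to deaths and survivors, and say how a death learned of after the Final Visit through SAE reporting is handled. Reconcile the 3-month Final Visit with the 120 days implied by Section 8.2.

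The cost is SAP wording and slightly less output. The sponsor gives up an exploratory median OS that this follow-up cannot support.

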10.1.2 Analysis of the antitumor activity endpoints

The analyses of the antitumor activity endpoints in Part B will be performed for the PPS. As a sensitivity analysis, all analyses will be repeated for the SS. All listings will be presented for the SS. Summaries and listings will be presented by treatment group.

All lesion assessment data recorded at Baseline (Screening) and during the Treatment Period (every 8 weeks from Day 1 of Cycle 1 [± 7 days]) will be listed separately for target lesions, non-

target lesions and new lesions. Each post-Baseline tumor assessment will be labelled as ‘Tumor Assessment 1, Tumor Assessment 2 etc. – see further details below). These listings will include lesion number and lesion type (nodal/non-nodal), location, method of assessment, dimension (or an indication that the lesion is too small to measure, for target lesions only) and lesion response evaluation (for non-target lesions at post-Baseline assessments). The listing for target lesions will also include the derived eCRF component data used for the determination of the overall target lesion response at each post-Baseline assessment (e.g. sum of all dimensions across target lesions and percentage change from Baseline in the sum). In addition, the overall response assessment for target lesions and non-target lesions, as determined by the investigator, will be listed for each post-Baseline tumor assessment (Tumor Assessment 1, Tumor Assessment 2 etc.) together with the presence of new lesions and the overall response assessment.

The investigator's overall tumor response assessment will be summarized using frequency counts and percentages over time (tumor assessment). Post-Baseline tumor assessments are scheduled to be performed per protocol every 8 weeks from Day 1 (± 7 days). For the purpose of this summary, the first post-Baseline tumor assessment (scheduled or unscheduled) will be assigned to ‘Tumor Assessment 1’ using the protocol-defined window of Day 50 to 64 (Day 57 ± 7 days) relative to Day 1 (first dose of UCB6114). For all subsequent post-Baseline tumor assessments (scheduled or unscheduled, but excluding tumor assessments performed at the SFU visit), these will be assigned to ‘Tumor Assessment 2’, ‘Tumor Assessment 3’ etc. using the protocol-defined window of Day 50-64 relative to the previous post-Baseline tumor assessment. If a post-Baseline tumor assessment is missed, then the scheduled day of the missed assessment will be used to window the next tumor assessment. In cases where a scheduled and unscheduled tumor assessment occurs in the same window, the investigator's overall tumor response at both assessments will be considered. If the overall tumor response is NE at one of the assessments, then the overall tumor response from the other assessment will be included in the summary table. If the overall tumor response is not NE at both assessments, then the tumor assessment that is closest to the target day of the tumor assessment will be included in the summary table. In the event that the two tumor assessments are equidistant from the target day of the tumor assessment and neither have an overall tumor response of NE, then the worst case overall tumor response will be included in the summary table. Otherwise, if the post-Baseline tumor assessment falls outside of the protocol-defined window, it will be classified as an unscheduled assessment and not included in the summary of overall tumor response.

Bar charts will also be produced for overall tumor response rate by treatment group for each visit. In addition, waterfall plots of participants' percentage change from Baseline in the sum of dimensions for all target lesions will be presented by treatment group and visit. The individual participants' bars will be colored by overall tumor response at the visit.

Confirmed and unconfirmed BOR for each participant will be derived programmatically using the investigator's overall tumor response assessments (scheduled and unscheduled) performed every 8 weeks from Day 1 of Cycle 1 (or at unscheduled timepoints) and the RECIST criteria. Whether a BOR of CR or PR is confirmed or unconfirmed will be indicated on this listing. Using a participant's confirmed BOR and unconfirmed BOR, whether the participant achieves an objective tumor response (i.e. a BOR of CR or PR) and/or disease control (i.e. a BOR of CR, PR or SD) during study treatment will be determined. These derived data will be listed for the SS.

Confirmed and unconfirmed BOR will be summarized using frequency counts and percentages. Bar charts will also be produced for confirmed BOR and unconfirmed BOR by treatment group.

The number and percentage of participants achieving objective tumor response and disease control (ORR and DCR) based on confirmed BOR and BOR (confirmed or unconfirmed) will be presented and, if data allow, exact 95% CIs for binomial proportions will be calculated using the Clopper-Pearson method and presented for the response rates. In the calculation of ORR and DCR, the denominator will include all participants in the analysis set. Objective response rate and DCR (based on confirmed BOR and unconfirmed BOR) will also be summarized in bar charts by treatment group overall and by tumor type and ECOG performance status at Baseline.

In addition, waterfall plots of each participant's best percentage change from Baseline in the sum of the dimensions for all target lesions will be presented by treatment group overall and by tumor type and ECOG performance status at Baseline with the individual participants' bars colored by confirmed BOR and unconfirmed BOR.

The summaries and analyses of DOR, PFS and OS will be carried out as described below, if the data allow.

Duration of confirmed response, DOR (confirmed or unconfirmed) and PFS will be listed and summarized descriptively using Kaplan-Meier estimation. These summaries will be repeated for the sensitivity analyses of these endpoints (defined in [Section 10.1.1](#) above) and will include the number and percentage of participants with the event, the number and percentage of participants censored, minimum and maximum values and Kaplan-Meier estimates of the 25th percentile, median, 75th percentile and corresponding 95% CIs calculated using Greenwood's formula. In addition, DOR and PFS rates at 3 months, 6 months and 9 months will be derived from the Kaplan-Meier estimation and presented together with associated 95% CIs.

Kaplan-Meier curves will be presented for duration of confirmed response and DOR (confirmed or unconfirmed) and PFS. Treatment groups will be overlaid on each plot.

Survival status collected on the eCRF at the SFU visit and at the Final Visit will be listed for each participant by treatment group. This listing will include the participant's survival status, date and cause of death, whether an autopsy was performed and date of autopsy, whether the participant had received any further antitumor treatment after the last dose of study treatment and the type of treatment, and whether the participant's disease had been assessed since the end of study treatment including method of assessment and the overall response.

Overall survival times will be listed and summarized descriptively using Kaplan-Meier estimation. Note that since participants are only followed up for survival until the Final Visit in Part B of the study, a summary of OS may not be meaningful (i.e. if no participants die then OS cannot be assessed).

Exploratory analyses of selected antitumor activity endpoints may be performed based on subgroups of participants in the SS. Data permitting, the subgroups will be defined based on participant, disease, and treatment history information (e.g. extent of prior anti-cancer therapy).

Additionally, the relationship of the antitumor activity variables with key PK parameters may be explored but this will be reported separately.

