3. DATA ANALYSIS CONSIDERATIONS

3.1 General presentation of summaries and analyses

All TFLs will be produced by ICON PLC using SAS® Version 9.4 or higher (SAS Institute, Cary, North Carolina, USA). ICON PLC will also produce the analysis datasets which will adhere to the Clinical Data Interchange Standards Consortium (CDISC) guidance documents for Analysis Data Model (ADaM) and follow the Sponsor's interpretation. General statistical and reporting conventions will follow the current UCB Global Conventions Document Version 1.1.

Data will be summarized by UCB6114 dose level (treatment group), visit and timepoint, as applicable. All relevant reported and derived data will be listed and will be presented by treatment group, study participant and visit, as applicable.

Categorical variables will be summarized using frequency counts and percentages. Unless otherwise stated, the denominator for the percentages will be based on the number of participants in the respective analysis set, treatment group, visit and timepoint (as applicable) with non-missing data.

When reporting frequency counts and percentages, the following rules apply:

- For categories where all participants fulfill certain criteria, the percentage value will be displayed as 100;
- For categories where zero participants fulfill certain criteria, there will be no percentage displayed;
- All other percentage displays will use 1 decimal place.

Summary statistics will be presented for continuous variables including number of participants (n), arithmetic mean, standard deviation, median, minimum and maximum. 95% confidence

intervals (CIs) for the arithmetic mean may also be included depending on the variable and where stated in the SAP. Geometric mean (geoMean), geometric coefficient of variation (geoCV) and 95% CI for the geoMean will also be presented in the summaries of UCB6114 concentration data. In all relevant outputs the 95% confidence limits will be restricted to the possible values that the variable can take.

When reporting descriptive statistics for data other than UCB6114 concentration data, the following rules will apply:

- n will be an integer;

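### The per-assessment tumor response percentages and per-visit response-rate bar charts have no stated denominator, so by default they are conditional on an in-window scan

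*SAP*

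**What the plan says.** Parts B and C carry the same rules; section numbers apply to both.

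- **Table.** Section 10.1.2 says of the investigator's response: "overall tumor response assessment will be summarized using frequency counts and percentages over time (tumor assessment"). No denominator is given.
- **Chart.** The same section adds: "Bar charts will also be produced for overall tumor response rate by treatment group for each visit". Neither numerator nor denominator is defined.
- **Default denominator.** Section 3.1 bases percentages, unless stated otherwise, on the number of "participants in the respective analysis set, treatment group, visit and timepoint (as applicable) with non-missing data".
- **Windows.** The first assessment is assigned "using the protocol-defined window of Day 50 to 64 (Day 57 ± 7 days"). Later ones are windowed from the previous assessment. Of a scan outside its window the section says: "it will be classified as an unscheduled assessment and not included in the summary of overall tumor response".
- **SFU scans.** Section 10.1.2 describes the later assessments as "scheduled or unscheduled, but excluding tumor assessments performed at the SFU visit". Section 4.3 applies the same exclusion to all post-Baseline assessments, so including the first.
- **Full-set denominator.** Section 10.1.2 states this only for ORR and DCR, which Section 10.1.1 defines from best overall response (BOR).
- **Follow-up and missing data.** Treatment continues until progression, toxicity or withdrawal of consent (Section 2.3). Missing data are not imputed unless a section says so (Section 4.2).

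**The concern.** Each rule is ordinary alone; together they fix an estimand that the output does not name. A participant with PD at Tumor Assessment 1 ordinarily has no in-window scan at Tumor Assessment 2 and leaves the denominator. A participant whose PD is found before Day 50, or only at the SFU visit, may not enter the table at all. What remains is response among those still being scanned on schedule.

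Dose levels have 3 to 9 evaluable participants, so a few departures move the percentage a long way. A dose level with more early progression could show a higher late response rate than one with less. Available antitumor activity is one of several inputs to the recommended Phase 2 dose in each Part (Section 2.3), so these charts may be read side by side across doses. Section 10.1.2 would also report two kinds of response rate on different denominators without saying so.

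**Working it through.** The SAP gives no figure for a per-visit rate, so there is none to reproduce. The check compares two denominators.

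**Inputs from the SAP.** Up to 9 evaluable participants per dose level (Section 2.3); first window Day 57 − 7 = 50 to Day 57 + 7 = 64 (Section 10.1.2); default denominator (Section 3.1).

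**Assumptions, not in the SAP.** The response and progression splits; responders stay in response; no new responses; progressors have no later in-window scan; the chart uses the same windowed assessments as the table.

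**Formulas at assessment k.**
- Default rate = responders at k / participants with an in-window result at k.
- Full-set rate = responders at k / all participants in the analysis set.

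**Main illustration: n = 9, with 2 PR, 3 SD and 4 PD at Tumor Assessment 1.**
- Assessment 1, both denominators: 2/9 = 22.2% (Clopper-Pearson 95% CI 2.8 to 60.0).
- Assessment 2, default: 2/(9 − 4) = 2/5 = 40.0% (5.3 to 85.3).
- Assessment 2, full set: 2/9 = 22.2%.

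**Range over the assumed split.**

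| Group size | Lasting responders | PD at Assessment 1 | Rate at Assessment 1 (also full-set rate at Assessment 2) | Default rate at Assessment 2 |
|---|---|---|---|---|
| 9 | 1 | 2 to 6 | 1/9 = 11.1% | 1/7 to 1/3 = 14.3% to 33.3% |
| 9 | 2 | 2 to 6 | 2/9 = 22.2% | 2/7 to 2/3 = 28.6% to 66.7% |
| 9 | 3 | 2 to 6 | 3/9 = 33.3% | 3/7 to 3/3 = 42.9% to 100% |
| 3 | 1 | 1 to 2 | 1/3 = 33.3% | 1/2 to 1/1 = 50% to 100% |

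**Effect of the window.** If 2 of 9 progress on a scan before Day 50, Assessment 1 reads 2/7 = 28.6% instead of 22.2%, and those two progressions appear nowhere in the table. With 3 further PD at Assessment 1, Assessment 2 reads 2/4 = 50.0%.

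**Effect of the SFU exclusion.** The SFU visit is about 30 days after the last dose. With a last dose on Day 29 it falls near Day 29 + 30 = Day 59, inside the first window. Under Section 4.3 a PD scan at that visit is still left out.

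**The other direction.** If one of the 2 responders leaves and nobody progresses, the default rate falls from 2/9 = 22.2% to 1/8 = 12.5%. The direction depends on who leaves.

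**The case against.** The case against is substantial on importance.

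- **Not endpoints.** The table and chart are not in the endpoint list of Section 2.2.3.1, and Section 10.1 calls the whole antitumor analysis exploratory. No escalation rule uses them. This stands and limits the weight of the point.
- **Progressions are captured elsewhere.** BOR, DOR and PFS use all scheduled and unscheduled scans (Section 4.3). BOR takes in assessments up to the SFU visit absent earlier progression or new therapy, and death without documented progression is a PFS event (Section 10.1.1). ORR and DCR use the whole analysis set. A reader might infer that early progressors vanish from the reported antitumor activity; they vanish only from this table and chart.
- **The window is date-based.** An out-of-window CR or PR is dropped too, and two in-window scans equidistant from the target day are settled by the worse result. A reader might infer that the rule selects on response; it does not. An unscheduled scan may be prompted by suspected progression, but the SAP says nothing on how often.
- **Observed-case tables by visit are common, and counts accompany the percentages.** True of the table. The chart plots a rate, and Section 10.1.2 requires neither the number assessed nor a conditional label on it.
- **The denominator is inferred.** Section 10.1.2 is silent, and a programmer could choose another. The inference follows the SAP's own default; otherwise the rate is simply undefined, which also needs correcting.

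**Conclusion.** The point holds in a limited form. As written, the per-assessment percentages and the per-visit rate are conditional on an in-window scan, and nothing in Section 10.1.2 says so. In the assumed group of 9 with 2 lasting responders, 2 to 6 progressors lift the second-assessment rate from 22.2% to between 28.6% and 66.7% with no new response. These sizes rest on assumed splits and on progressors having no later in-window scan.

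It would go too far to say that the rate climbs over time as a rule. The documents support only that it can rise when non-responders leave faster than responders, which treatment to progression favours; it can also fall. BOR, ORR, DCR and PFS stand as planned. This is a worthwhile correction to supplementary displays, not a flaw in an endpoint.

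**What to change.** In Section 10.1.2 of both Parts:

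1. Define the per-visit response rate as CR+PR at that tumor assessment, and say that the chart uses the same windowed assessments as the table.
2. Use all participants in the analysis set as the denominator for both (the PPS, and the SS in the sensitivity analysis).
3. Add a row for PD or death before this assessment, including PD from out-of-window or SFU scans. Set its cut-off at the end of that assessment's window and count nobody already in the PD row, so that an SFU scan dated inside the window has a place.
4. Add a row for not assessed or out of window, and show the number assessed at each assessment.
5. Label any rate kept on scanned participants as conditional on an in-window scan.

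In the main illustration, Assessment 2 would then read 2 PR, 3 SD and 4 with earlier PD, total 9. The added row counts known status; it does not impute a PD response at later assessments, so it does not conflict with Section 4.2.

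The cost is SAP wording and one table shell and one figure shell per Part, with no new data. Late percentages will look less favourable.
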